6.4 Electrocardiogram

P-R interval, QT interval, QRS duration, Ventricular heart rate and QTc intervals using Fridericia's correction formula will be investigated. QTc values will be used as reported, they will not be recalculated. Changes from baseline for all Electrocardiogram (ECG) parameters will be summarized at each scheduled timepoint (Days 3, 6 and 33) (Table 14.3.4.1). In addition, frequency tabulation of the overall ECG results (Normal, Abnormal NCS, and Abnormal CS) will be summarized (Table 14.3.4.2).

6.5 Physical Examinations

For physical examination data, when calculating the percentage reporting each category, the “Not Done” category will not be included in the denominator.

Number (%) of subjects with abnormal physical examinations will be tabulated at screening and Days 1, 3, 5 and 33 (Tables 14.3.5.1). Normal/abnormal shift from pre-dose at Day 1 to pre-dose at subsequent days will also be provided (Tables 14.3.5.2).

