4.2.2 SECONDARY ENDPOINTS

This study is not powered to detect statistically significant differences in cognitive domains between the baseline and end of study values. Secondary endpoints will be summarized over the study period from baseline values using descriptive statistics.

Secondary safety endpoints are as follows:

- Changes from baseline in clinical laboratory parameters.
- Changes from baseline in vital sign measurements.
- Changes in body weight from baseline to Visit 8.
- Changes from baseline in physical exam parameters at Visit 10 or End of Study/Early Termination.
- Changes from baseline in ECG recordings.

Secondary efficacy endpoints are as follows:

- Changes in the MMSE ([Folstein 1975, Appendix 1](#)).
- Changes in the SIB ([Paniiset 1994, Appendix 2](#)).
- Changes in the ADCS-ADL-Severe ([Galasko 2005, Appendix 3](#)).
- Changes in the ADCS-CGIC ([Ferris 1997, Schneider 1997, Appendix 4](#)).
- Change on the NPI/NPI-NH ([Cummings 1994, Wood 2000, Appendix 5](#)).

Secondary feasibility endpoints include:

- Subject compliance with the study visit schedule, procedures, infusions, and any required adaptations that are necessary for study completion.
- Success of blinding. This will be assessed based on all occurrences (intentional or unintentional) of unblinding of blinded study subjects or study personnel (e.g. investigators, medical providers, cognitive testing raters, the Sponsor or their representatives).

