7.1.1.1.8 Physical Examination

A complete physical examination will be performed to assess the following organ systems: skin, ears, nose, throat, head, eyes, lungs/chest, heart, abdomen, musculoskeletal, extremities, neurologic, and lymphatic systems. Height and weight will also be documented as specified in [Section 15 Schedule of Events](#).

7.1.1.1.9 12-Lead ECG

A 12-lead ECG will be performed after the subject has rested quietly for at least 5 minutes in a supine position. In some cases, it may be appropriate to repeat abnormal ECGs to rule out technical factors contributing to ECG artifacts or abnormality. It is important that leads are placed in the same positions each time for consistency. The overall conclusion with the interpretation of the ECGs will be recorded on the appropriate CRF. The interpretation of the ECGs will be recorded as normal, abnormal but not clinically significant (NCS), or abnormal and clinically significant (CS). Corrected QTc intervals will be calculated using Fridericia's correction formula.

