7.1.1.2.6 Physical Examination

Refer to [Section 7.1.1.8](#) for a description of the complete physical exam. The complete physical exam will be performed at Screening and repeated at End of Study (or Early Termination).

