7.3.4 TREATMENT

The treatment period includes a total of 5 infusions during Week 1. It is anticipated that sites will infuse subjects with 5 doses over 5 days. A “grace day” is allowed in the event of unanticipated safety or health concerns during the treatment period.

Visits 3 -7 (Days 1-5)

- Perform the following procedures prior to administering study treatment:
 - Review AEs and concomitant medications.
 - Obtain samples for proteomics/epigenetics/biobanking; fasting samples preferred (**Visit 3 Only**).
 - Obtain sample for ApoE genotype testing (**Visit 3 Only**).
 - Obtain pre-infusion safety laboratory samples and assess results **prior to the next day's infusion (Visits 4, 5, and 6 Only)**. (When using an i-STAT Handheld Blood Analyzer, the blood sample(s) may be obtained on the same day as the infusion, provided that all pre-infusion safety lab results are available and interpreted prior to the subject's infusion start on Visits 5, 6, and 7.)
 - Collect urine for urinalysis (**Visit 6 Only**).
 - Measure and record the subject's weight in kilograms.
 - Perform targeted physical exam (i.e. auscultation of heart and lungs and assessment of peripheral edema) (**Visits 3, 5, and 7 Only**).
 - Perform 12-lead ECG (**Visits 3 and 5 Only**).
 - Collect pre-infusion vital signs.
- Administer study treatment and perform safety assessments per the Infusion Administration Manual.

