10.4.4 ANALYSIS OF THE SECONDARY SAFETY ENDPOINTS

Actual values and changes from baseline in clinical laboratory measurements, vital signs, and body weight will be assessed and summarized. Abnormal lab or vital sign values will be determined and flagged in the listings. Laboratory shift tables or graphics displaying the change (number of subjects) relative to the reference range from baseline to each study visit may also be presented for each test. The investigator should exercise his or her medical and scientific judgment in deciding and documenting whether an abnormal

laboratory finding or other abnormal assessment is clinically significant.

For secondary safety endpoints that are continuous in nature (e.g. clinical laboratory parameters, systolic and diastolic blood pressure, heart rate, respiratory rate, temperature, body weight) the mean, median, minimum, maximum, and standard deviation will be plotted over time.

For secondary safety endpoints that are categorical in nature (e.g. physical exam or ECG abnormalities), the frequency counts and percentages will be presented as a descriptive summary.

Per-subject extent of exposure will be listed.

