2.3 Study Phase, Visit, and Day

The study is set up as shown above, along with study phase, visit, and day. In general, the baseline is defined as the last assessment before the first intake of the study medication unless otherwise specified. All scheduled assessments after first administration of study drug will be used.

Repeat/unscheduled assessments will not be used in descriptive statistics or any per-time point analyses but will be shown in listings as applicable. Pre-dose unscheduled assessments will be taken into account for baseline determination and post first dose unscheduled assessments will be taken into account for worst-case determination as applicable.

Reference date refers to the start date of the first study drug administration. All efficacy and safety assessments at all visits will be assigned a day relative to this date. The relative day will be defined as: visit date – reference date + 1 for visits on or after the reference date and visit date – reference date for visits before the reference date. Consequently, there is no 'Day 0' defined.

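### SAP 6.5 starts the physical-exam shift table from the Day 1 targeted exam, so no planned table shows the within-subject change from Screening to Visit 10

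*SAP*

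**What the plan says.** Protocol 4.2.2 lists this secondary safety endpoint: "Changes from baseline in physical exam parameters at Visit 10 or End of Study/Early Termination".

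The protocol has two kinds of physical exam:

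- **Complete exam.** Section 7.1.1.1.8 names the systems covered: "skin, ears, nose, throat, head, eyes, lungs/chest, heart, abdomen, musculoskeletal, extremities, neurologic, and lymphatic systems". Section 7.1.1.2.6 gives the timing: "The complete physical exam will be performed at Screening and repeated at End of Study (or Early Termination".
- **Targeted exam.** Section 7.3.4 places it before infusion at Visits 3, 5 and 7 (Days 1, 3 and 5) and gives its content: "Perform targeted physical exam (i.e. auscultation of heart and lungs and assessment of peripheral edema".

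For categorical safety endpoints, with physical-exam abnormalities named as an example, protocol 10.4.4 says that "the frequency counts and percentages will be presented as a descriptive summary".

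SAP 6.5 plans two tables. Table 14.3.5.1 is a frequency table: "Number (%) of subjects with abnormal physical examinations will be tabulated at screening and Days 1, 3, 5 and 33". Table 14.3.5.2 is a shift table: "Normal/abnormal shift from pre-dose at Day 1 to pre-dose at subsequent days will also be provided". Listing 16.2.10 lists the physical examinations for the Safety set.

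**The concern.** The endpoint is a change, and its visit is Visit 10 or Early Termination. The only planned table that pairs a subject's results over time starts from an exam of three areas and, as worded, stops before the endpoint's visit. The complete exam, which is the only one that looks at skin, abdomen, neurologic status and most other systems, is never paired with itself.

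Two things follow. First, the summary output cannot separate an abnormality that persisted from Screening from one that arose after dosing. Second, a programmer who tries to repair the table by adding Day 33 to it could create apparent new findings that were present before the first infusion.

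SAP 8 records no change to this endpoint. SAP 6.3 uses nearly the same wording for vital signs and weight, where it fits because those are measured before each infusion. The wording in 6.5 therefore looks inadvertent.

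**Working it through.** The plan gives no figure to reproduce, so the check is which exam exists at which visit and which table uses it.

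| Visit | Exam done | Table 14.3.5.1 (frequencies) | Table 14.3.5.2 (shift), as worded |
|---|---|---|---|
| Screening | Complete | Yes | No |
| Day 1 (Visit 3) | Targeted | Yes | Reference |
| Day 3 (Visit 5) | Targeted | Yes | Yes |
| Day 5 (Visit 7) | Targeted | Yes | Yes |
| Day 33 (Visit 10) | Complete | Yes | No: no dose, so no pre-dose exam |
| Early Termination | Complete | Not named | Not named |

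**Step 1: literal reading.** Dosing is on Days 1 to 5 (protocol 6.1.7). The later pre-dose exams are those of Days 3 and 5. Visit 10 is absent from the shift table for every system.

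**Step 2: systems with a Day 1 reference, if the table is by organ system.** The complete exam lists 13 systems.

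- Heart, lungs/chest, and extremities through the edema check: 3 covered. 13 − 3 = 10 without a reference; 10/13 = 77%.
- Edema not counted as an extremities exam: 2 covered. 13 − 2 = 11 without a reference; 11/13 = 85%.

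**Step 3: what the separate counts can show.** New abnormalities = abnormal at Day 33 − abnormal at both visits. As a hypothetical case, take 13 subjects on active treatment (20 × 2/3 = 13.3), with 3 abnormal at Screening and 3 at Day 33. The number abnormal at both visits can be anything from 0 to 3.

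- All 3 persistent: 3 − 3 = 0 new.
- None persistent: 3 − 0 = 3 new, or 3/13 = 23%.

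Table 14.3.5.1 would look the same in both cases.

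**Step 4: Day 33 added to the Day 1 table as one overall normal/abnormal result.** Suppose the 3 findings at Screening are all outside heart, lungs and edema, and all persist. On Day 1 these subjects are recorded as normal, because the affected system is not examined. On Day 33 they are recorded as abnormal. The table shows 3 shifts from normal to abnormal when the true number is 0.

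**Step 5: Screening as the reference.** The same complete exam is scheduled at Screening and at Visit 10, so like-for-like pairs are available for 13 of 13 systems.

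**The case against.** The case that little is missing has five parts.

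- **The protocol's summary is met.** Section 10.4.4 asks for counts and percentages, and Table 14.3.5.1 gives them at Screening and Day 33. The protocol requires no shift table for the physical exam. This stands. A reader might infer that the Visit 10 endpoint is not produced at all; the documents do not support that. What is missing is the paired change.
- **Subject-level data are available.** Listing 16.2.10 shows each exam, and with about 20 subjects a reader can compare Screening and Day 33 by eye. This also stands. The gap is in the summary output.
- **Important new findings are caught elsewhere.** Under protocol 8.1.1, a clinically significant change on physical examination that was absent at baseline or worsened is an adverse event, so it enters the treatment-emergent tables. A reader might infer that new safety signals would be lost. The documents point the other way: the loss falls mainly on findings not judged clinically significant.
- **The general rules would supply the reference.** SAP 2.3 says "the baseline is defined as the last assessment before the first intake of the study medication unless otherwise specified", which is Screening for systems examined only then, and SAP 2.6 calls for every planned timepoint in change tables. This is only a partial answer. The rule in 2.3 gives way to a specific rule, and 6.5 names Day 1. For a single overall result, the Day 1 targeted exam is itself the last one before dosing. Adding Day 33 under 2.6 then leads to the mismatch in Step 4.
- **The layout is unknown.** SAP 6.5 does not say that the shift is by organ system, and the table shells are a separate document. The count of 10 of 13 is therefore conditional and cannot be read as a property of the plan.

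**Conclusion.** The point holds as a minor one. As written, SAP 6.5 plans no table that gives the within-subject change from Screening to Visit 10 or Early Termination, although that change is the listed endpoint. The Day 1 targeted exam is also the wrong reference for the complete exam under either layout. By organ system, 10 of 13 systems (11 on the stricter mapping of edema) have no Day 1 value. As one overall result, an exam of three areas would be set against one of 13 systems.

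This rests on reading the shift sentence literally, so that a day without a dose has no pre-dose exam. The subject numbers in Steps 3 and 4 are illustrative. The primary endpoint, the sample size and the capture of adverse events are unaffected.

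**What to change.** In SAP 6.5 and the shell for Table 14.3.5.2:

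- Specify a normal/abnormal shift from the Screening complete exam to Day 33 or Early Termination, by organ system, and say how Early Termination exams are placed.
- Keep the Day 1 pre-dose reference only for the targeted items (heart, lungs, peripheral edema) on Days 3 and 5.
- Leave Table 14.3.5.1 and Listing 16.2.10 as they are.

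The cost is a few lines of SAP text and one table shell. No new data are needed, because the complete exam is already scheduled at both visits.

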7 EXPLORATORY

All exploratory analyses will be described in a separate plan.

8 CHANGES FROM PROTOCOL

The Per Protocol dataset is defined in the protocol as: a subset of the Evaluable Dataset comprised of subjects who have no Major Protocol Deviations. All failed eligibility criteria are considered a Major Protocol Deviation, however, not all eligibility criteria failures should automatically remove a subject from the Per Protocol dataset. This SAP clarifies which protocol deviations will exclude a subject from the per protocol dataset and all protocol deviations will be reviewed by the study team prior to database lock to identify the final Per Protocol dataset definition

Blood pressure values that constituted an AESI were at the discretion of the PI. As such, ranges for blood pressures of special interest (BPSI) were identified and will be analyzed according to section 6.3

Table 14.1.7.4	Overall infusion parameters per infusion day	SAF
Table 14.1.8.1	Completion of Study Drug	SAF
Table 14.1.8.2	Number of subjects completing 5 infusions	SAF
Table 14.1.9	Number of subjects completing 4 weeks after receiving at least 5 infusions	SAF
Table 14.1.10	Visit Compliance	SAF
Table 14.2.1	Changes in scores on the Mini-Mental State Examination (MMSE)	EVAL, PPROT
Table 14.2.2	Changes in scores on the Severe Impairment Battery Total score	EVAL, PPROT
Table 14.2.3	Changes in the Alzheimer's Disease Cooperative Study – Activities of Daily Living Severe (ADCS-ADL Severe)	EVAL, PPROT
Table 14.2.4	Alzheimer's Disease Cooperative Study – Clinical Global Impression of Change (ADCS-CGIC)	EVAL, PPROT
Table 14.2.5	Change on the Neuropsychiatric Inventory Questionnaire (NPI or NPI-NH) total severity score and total distress score	EVAL, PPROT
Table 14.3.1.1	Overall Summary of Treatment-Emergent Adverse Events (TEAE)	SAF

Number	Title	Population
Table 14.3.1.2.1	Incidence of Treatment-Emergent Adverse Events (TEAEs) by MedDRA System Organ Class and Preferred Term	SAF
Table 14.3.1.2.2	Incidence of Treatment-Emergent Adverse Events (TEAEs) by MedDRA Preferred Term	SAF
Table 14.3.1.3	Incidence of Treatment-Emergent Adverse Events (TEAEs) by Severity and MedDRA System Organ Class and Preferred Term	SAF
Table 14.3.1.4	Incidence of Treatment-Emergent Adverse Events (TEAEs) by Relationship to Study Drug and MedDRA System Organ Class and Preferred Term	SAF
Table 14.3.1.5.1	Incidence of Serious Treatment-Emergent Adverse Events (TEAEs) by MedDRA System Organ Class and Preferred Term	SAF
Table 14.3.1.5.2	Incidence of Treatment-Emergent Adverse Events (TEAEs) of Special Interest by MedDRA System Organ Class and Preferred Term	SAF
Table 14.3.1.5.3	Incidence of Treatment-Emergent Adverse Events (TEAEs) Leading to Subject Withdrawal by MedDRA System Organ Class and Preferred Term	SAF
Table 14.3.1.5.4	Incidence of Treatment-Emergent Adverse Events (TEAEs) Leading to Death by MedDRA System Organ Class and Preferred Term	SAF
Table 14.3.1.6.1	Listing of Serious Treatment-Emergent Adverse Events (TEAEs)	SAF
Table 14.3.1.6.2	Listing of Treatment-Emergent Adverse Events (TEAEs) of Special Interest	SAF
Table 14.3.1.6.3	Listing of Treatment-Emergent Adverse Events (TEAEs) Leading to Subject Withdrawal	SAF
Table 14.3.1.6.4	Listing of Treatment-Emergent Adverse Events (TEAEs) Leading to Death	SAF
Table 14.3.2.1.1	Changes in hematology measurements	SAF
Table 14.3.2.1.2	Changes in serum chemistry measurements	SAF
Table 14.3.2.1.3	Changes in urinalysis measurements	SAF
Table 14.3.2.3.1	Shift Table in hematology measurements	SAF

Number	Title	Population
Table 14.3.2.3.2	Shift Table in serum chemistry measurements	SAF
Table 14.3.2.3.3	Shift Table in urinalysis measurements	SAF
Table 14.3.3.1	Changes from baseline in vital sign measurements and weight	SAF
Table 14.3.3.2	Changes from pre-dose in vital sign measurements within each infusion day	SAF
Table 14.3.3.3	Blood pressure changes of special interest	
Table 14.3.4.1	Changes from baseline in ECG measurements	SAF
Table 14.3.4.2	Frequency of overall ECG results	SAF
Table 14.3.5.1	Frequency of abnormal physical examination results	SAF
Table 14.3.5.2	Shift Table in physical examination results	SAF

11 LISTINGS FOR CSR APPENDIX 16.2

Number	Title	Population
Listing 16.2.1.1	Analysis Populations	SCRN
Listing 16.2.1.2	Screen Failures	SCRN
Listing 16.2.1.3	Subject Disposition	ITT
Listing 16.2.1.4	Protocol Deviations	ITT
Listing 16.2.1.5	Informed Consent	ITT
Listing 16.2.1.6	Study Visits	ITT
Listing 16.2.2.1	Inclusion Criterion Not Met or Exclusion Criteria Met	ITT
Listing 16.2.2.2	Randomization	ITT
Listing 16.2.3.1	Demographics	ITT
Listing 16.2.3.2	Baseline Characteristics	ITT
Listing 16.2.3.3	Baseline Assessment of Modified Hachinski Ischemia Scale (MHIS)	ITT
Listing 16.2.3.4	APOE Genotype	ITT
Listing 16.2.3.5	Echocardiogram	ITT
Listing 16.2.4.1.1	Medical History	SAF
Listing 16.2.4.1.2	Alzheimer's Disease History	SAF
Listing 16.2.4.2	Family Medical History	SAF
Listing 16.2.4.3	Social History	SAF
Listing 16.2.4.4	Tobacco Use	SAF
Listing 16.2.4.5	Alcohol and Illicit Substance Use	SAF
Listing 16.2.4.6	Echocardiogram Results	SAF
Listing 16.2.5.1.1	Prior Medications	SAF
Listing 16.2.5.1.2	Previous Treatment for Alzheimer's Disease	SAF
Listing 16.2.5.2	Concomitant Medications	SAF
Listing 16.2.5.3	Extent of Exposure	SAF
Listing 16.2.5.4	Infusion Rate	SAF
Listing 16.2.5.5	Daily Summary of Infusion Administration	SAF
Listing 16.2.5.6	Treatment Completion	SAF
Listing 16.2.5.7	Tolerability	SAF
Listing 16.2.5.8	Assessment of Blinding	SAF
Listing 16.2.6.1	Mini-Mental State Examination (MMSE)	ITT
Listing 16.2.6.2	Severe Impairment Battery	ITT
Listing 16.2.6.3	Alzheimer's Disease Cooperative Study – Activities of Daily Living Inventory for Severe Alzheimer's Disease (ADCS-ADL Severe)	ITT
Listing 16.2.6.4	Alzheimer's Disease Cooperative Study – Clinical Global Impression of Change Caregiver Input rating (ADCS-CGIC)	ITT
Listing 16.2.6.5	Neuropsychiatric Inventory Questionnaire (NPI or NPI-NH)	ITT

Number	Title	Population
Listing 16.2.7.1	Non-Treatment Emergent Adverse Events	SAF
Listing 16.2.7.2	Treatment Emergent Adverse Events	SAF
Listing 16.2.8.1	Clinical Laboratory Results	SAF
Listing 16.2.8.2	ECG Results	SAF
Listing 16.2.9	Vital Signs	SAF
Listing 16.2.10	Physical Examinations	SAF

12 ATTACHMENTS

None
